To determine the effect of the administration of BBR, bezafibrate and BBR plus bezafibrate on body weight, height, body mass index (BMI), waist circumference, blood pressure, fasting glucose, creatinine, uric acid.

Describe the tolerability of the administration of BBR, bezafibrate and BBR plus bezafibrate.

METHODOLOGY

To assess the effect of the administration of the combination of BBR plus bezafibrate on the lipid profile in patients with mixed dyslipidemia.

Specific objectives

Determine the concentration of CT, TG, HDL-C, LDL-C, and VLDL-C before and after the intervention with BBR, bezafibrate and BBR plus bezafibrate.

Study design

Single randomized, parallel group, double-blind clinical trial. Resident population of the Guadalajara Metropolitan Area between 30 and 60 years of age, of any sex, with a diagnosis of mixed dyslipidemia.

Study site

Institute of Experimental and Clinical Therapeutics (INTEC) located in the Department of Physiology, University Center for Health Sciences, University of Guadalajara.

The sample size was calculated according to the formula for clinical trials, 61 in which the following values were taken into account for its calculation: The Z_α corresponds to the value of statistical confidence, which was prefixed to a value of $Z_{1-\beta}$ of 95%, for a type I error of 5% expressed as a value of 0.05 with two tails. For this confidence, the value of Z was 1.96.

$Z_{1-\beta}$ that expresses the statistical power or power and was prefixed to the value of $Z-\beta$ of 80%, for a type II error of 20%, which is equivalent to a value of 0.20. For this statistical power and this type II error, the typified Z score was 0.842.

The expression δ refers to the standard deviation in the basal TG concentrations obtained from the BBR studies, which was 35 mg / dL.62 d is the expected TG difference of 44.2 mg / dl.36

The result was $n = 10$ for each intervention group, in order to ensure sufficient statistical power, the sample size was increased by 20% due to possible losses, giving $n = 12$ patients per group.

Inclusion criteria

The study population was selected based on the fulfillment of the following criteria:

Men and women, age completed: 30 to 60 years residents of the Guadalajara metropolitan area, ability to communicate and comply with the established requirements.

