Kruskal-Wallis test to identify differences between the three intervention groups in relation to the quantitative variables of the included participants.

Wilcoxon rank test to identify differences between the baseline and final evaluation of each intervention group in relation to the quantitative variables of the included participants.

Mann-Whitney U test to identify differences between two intervention groups in relation to the quantitative variables of the included participants.

X² test or Fisher's exact test to identify differences between two intervention groups in relation to the qualitative variables of the included participants.

The preset level to consider the probability obtained from any of the statistical methods used was $p \leq 0.05$.

All variables were analyzed with the SPSS v22 program for windows.

Recruitment

15 detection campaigns were carried out in different points of the metropolitan area of Guadalajara, in which 290 people were attended, who were asked if they suffered or were referred to suffer from any cardiovascular disease, dyslipidemia, diabetes, prediabetes, etc. They were determined if they had obesity by calculating the BMI and the WC was determined; A capillary glucose test was also taken, for which a One touch ultra-glucometer was used to discard, by way of scrutiny, any alteration related to glucose metabolism.

Of these patients, 60 reported having a dyslipidemia reference of their own or of a direct relative and were invited to the INTEC located at the University Center for Health Sciences of the University of Guadalajara to carry out a more complete scrutiny.

Scrutiny

Each patient was summoned to INTEC at 08:00 am with a 12-hour fast. The visit during the scrutiny period, like the rest of the scheduled visits, took place at INTEC from 8 a.m. During the first visit, a complete clinical record was integrated, for which a clinical interrogation and comprehensive physical examination were carried out, all the clinical characteristics required for the evaluation of the selection criteria for admission were corroborated. 5 ml of

venous blood were taken by venipuncture with an 18 Gy catheter in the brachial vein to determine the lipid profile (CT, TG, HDL-C) and glucose.

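### Twelve per arm covers the loss of 2 of 12, not 20%, and the normal-approximation formula somewhat overstates power at 10 evaluable per arm

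*Combined protocol and SAP*

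**What the plan says.** The sample size paragraph, in Methodology under Study site, sets out its inputs one by one. The significance level is "for a type I error of 5% expressed as a value of 0.05 with two tails", and "For this confidence, the value of Z was 1.96". Power is 80%, "for a type II error of 20%, which is equivalent to a value of 0.20", and "the typified Z score was 0.842". The spread is "the standard deviation in the basal TG concentrations obtained from the BBR studies, which was 35 mg / dL", and the TG difference to be detected is 44.2 mg/dL. The result is 10 per group. To protect power, "the sample size was increased by 20% due to possible losses", which brings it to 12. No dropout rate is stated in any other form.

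The Statistic Analysis Plan reports that TG failed a normality test and that non-parametric methods were therefore used. For pairs of arms it names the "Mann-Whitney U test to identify differences between two intervention groups". It does not say whether p-values are exact or asymptotic. Under Groups, intervention allocation and blinding, anyone who took at least one dose is kept in the analysis, with no method for a missing final value.

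**The concern.** Losses are taken from the patients enrolled, so an allowance for a loss fraction L divides by 1 - L; it does not multiply by 1 + L. Adding 20% to 10 gives 12, and 20% off 12 leaves fewer than the 10 the plan says it needs.

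Separately, the formula treats the test statistic as normal with known variance. With 10 or so per arm, that approximation flatters a t-test and is not matched to a rank test.

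The stated 80% is the figure against which a non-significant comparison of the combination with a single agent would be read. If it is too favourable, such a result looks more informative than it is.

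**Working it through.** **Inputs.** Two-sided alpha 0.05 (z = 1.96), power 80% (z = 0.842), SD 35, d = 44.2; 10 per arm, then 12. All come from the sample size paragraph.

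**Reproducing the plan's figure.** n = 2(1.96 + 0.842)² × 35² / 44.2² = 2 × 7.851 × 1225 / 1953.64 = 9.85, rounded up to 10. Then 10 × 1.2 = 12. Both figures reproduce.

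**Loss allowance.**
- Left after a 20% loss from 12: 12 × 0.8 = 9.6.
- Needed to keep 10 after a 20% loss: 10 / 0.8 = 12.5, so 13.
- Loss that 12 absorbs while keeping 10: 2/12 = 16.7%.

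**Cost of that slip by the plan's own formula.** Power = Φ[(d/SD)√(n/2) − 1.96].
- n = 10: Φ(2.824 − 1.96) = 80.6%.
- n = 9.6: Φ(2.767 − 1.96) = 79.0%.

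So the slip costs about 1 point below the 80% target, and one patient per arm.

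**Small-sample power, same d, SD and alpha.** The t-test figures use the noncentral t distribution with 2n − 2 degrees of freedom and noncentrality (d/SD)√(n/2). The Mann-Whitney figures are simulated on normal data (40,000 runs).

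| n per arm | Plan's formula | t-test | Mann-Whitney, exact p | Mann-Whitney, asymptotic p |
|---|---|---|---|---|
| 9 | 76.4% | 71.1% | 65% | 69% |
| 10 | 80.6% | 76.1% | 72% | 75% |
| 11 | 84.2% | 80.4% | 78% | 78% |
| 12 | 87.1% | 84.0% | 81% | 82% |

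At 10 per arm the approximation exceeds the t-test by 80.6 − 76.1 = 4.5 points. This gap is there whatever the loss rule.

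**Dependence on shape.** The documents give no distribution for TG, so the shapes here are assumptions. With SD 35, a location shift of 44.2 and exact p, simulated Mann-Whitney power at 10 per arm is about 71-72% for normal data, 73% for a mildly skewed lognormal, 79% for a t with 5 degrees of freedom, 80% for a gamma with shape 2, and 85% for an exponential.

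**Dependence on SD.** The Background reports TG of 215.9 ± 64.7 before and 131.1 ± 51.2 mg/dL after treatment in a berberine trial. By the plan's formula with d = 44.2:
- SD 51.2: 2 × 7.851 × 51.2² / 44.2² = 21.1, so 22 per arm.
- SD 64.7: 2 × 7.851 × 64.7² / 44.2² = 33.6, so 34 per arm.

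At 12 per arm the formula then gives 56% and 39% power.

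**The case against.** The strongest reply is that the plan did what it says. Its formula gives 10 with 80.6% power, and adding 20% to 10 gives 12. Read as two spare patients per arm, the allowance leaves exactly 10, and no 20% dropout rate is expressly asserted. This stands, and it limits the first part to a matter of how the allowance is described.

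A second reply is that the Mann-Whitney figures in the low 70s assume normal data, although the plan chose rank tests because TG was not normal. With marked skew or heavy tails the same test can reach 80% at 10 per arm, and asymptotic p-values add about 3 points even with normal data. This also stands: no single Mann-Whitney figure can be presented as fact. It does not rescue the stated 80%, because the formula rests on a normal model, and under that model the t-test has 76% at 10.

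A third reply is that early leavers stay in the analysis. That helps little, since a patient without a day-90 sample adds no final TG unless a value is filled in, and no method is given.

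A reader might infer three stronger things. One is that the loss rule causes the fall to 72-76%. It does not: by the plan's formula it costs about 1 point, and the rest comes from the choice of test at a small sample size. Another is that 80% power survives only if nobody is lost. The documents do not support that: the t-test has 80.4% at 11 per arm and the plan's formula 80.6% at 10. The third is that power should be judged at a multiplicity-adjusted level. The plan sets 0.05 with no correction, and whether it should correct is a separate question.

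**Conclusion.** The point holds in a limited form. The allowance covers 2 of 12 (16.7%) per arm, not 20%; by the plan's own calculation the difference is one patient per arm and about 1 point of power. Independently, 80% at 10 evaluable per arm is about 4 points too high for a t-test under the formula's own normal model. For the planned Mann-Whitney test the shortfall is about 5 to 9 points if TG is normal, and may vanish if TG is markedly skewed or heavy-tailed. With all 12 per arm evaluable, power is at or above 80% by either test on normal data.

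These figures are for one pairwise comparison at two-sided 0.05, with d = 44.2 and SD 35 taken as given. The SDs in the plan's own Background would lower power far more than either issue here.

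**What to change.** Keep 12 per arm, replace the statement about the allowance for losses, and restate the power in words such as these:

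> Twelve per arm allows for loss of up to 2 of 12 (16.7%) per arm. For a 44.2 mg/dL difference with SD 35 and two-sided 0.05, power for a single pairwise comparison, assuming normal data, is about 84% (t-test) or 81% (exact Mann-Whitney) with no losses, and about 76% or 72% with 10 evaluable per arm. Mann-Whitney power differs if TG is skewed.

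Add a sentence saying that all these figures depend on SD 35 and that the Background cites TG SDs of 64.7 and 51.2 mg/dL. The cost is a slightly less favourable stated power. No extra patients are needed and nothing in the conduct of the trial changes.

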Diagnosis of mixed dyslipidemia ($TG \geq 150 \text{ mg / dL}$ and $TC \geq 200 \text{ mg / dL}$), No drug treatment on lipid profile, signing of the consent letter under information.

People with suspected or confirmed pregnancy, lactating or puerperium, $TC \geq 400 \text{ mg / dL}$ were not included, $TG \geq 500 \text{ mg / dL}$, $BMI \geq 39.9 \text{ kg / m}^2$, DM2, Kidney and / or liver disease, Intolerance to bezafibrate or BBR, PAS / DBP $\geq 140 / 90 \text{ mmHg}$, consumption of drugs with known action on lipid profile, glucose metabolism, BP or body weight.

Elimination criteria. The withdrawal of informed consent, loss of follow-up, presence of a serious adverse event, adherence to treatment $<80\%$ were considered as a reason for exclusion, but not so in the final statistical analysis. Presence of any non-inclusion criteria during the intervention.

Variables

Independent variable

Pharmacological intervention:

Administration of 1500 mg of BBR homologated with 400 mg of placebo (calcined magnesia)

Administration of 400 mg of approved bezafibrate with 1500 mg of placebo (calcined magnesia)

Administration of 1500 mg of BBR with 400 mg of bezafibrate

Dependent variables

Primary: lipid profile (TC, TG, LDL-C, HDL-C, VDL)

Secondary: weight, height, BMI, WC, BP, glucose, creatinine and uric acid, as well as tolerability

Control variables

Diet: They were given general nutrition recommendations based on the provisions of the dietary and physical activity recommendations of the National Academy of Medicine of Mexico, as shown in ANNEX document.

Exercise: They were asked to continue with the daily physical activity they already did and not to increase it.

The patients who came voluntarily for clinical evaluation generally had some cardiovascular risk factor such as dyslipidemia, smoking, etc.

Groups, intervention allocation and blinding

Three groups were formed randomly which were integrated in the following way.

The first group of 12 patients with mixed dyslipidemia received O.V. one 500 mg BBR capsule and one 500 mg placebo capsule at breakfast, one 500 mg BBR capsule at lunch, and one BBR capsule and one 500 mg placebo capsule at night.

The second group of 12 patients with mixed dyslipidemia received one 200 mg bezafibrate capsule in the morning and one 500 mg placebo capsule, one 500 mg placebo capsule with food, and one 200 mg bezafibrate capsule and one of 500 mg placebo in the evening.

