The 60 patients who were attended with the intention of knowing whether or not they suffered from mixed dyslipidemia, after carrying out the laboratory procedures, the results showed that 21 patients did not suffer from mixed dyslipidemia, so they did not continue as part of the study, however they were offered nutritional care by nutrition staff. Of the 39 who met the criteria for mixed dyslipidemia, 3 decided not to participate in the study and 36 agreed to participate; They were explained in detail each of the aspects of the project, the consent letter was read and explained under detailed information and they were asked to come the next day or the third day to begin their inclusion in the study and thus have a scheduled visit cycle for each one.

Intervention period

Through the indicated laboratory tests, each of the biochemical selection criteria was identified and documented. The patient who met the inclusion criteria was assigned to one of the intervention groups.

Visit 1. Participants who met the inclusion criteria, signed the consent letter and agreed to participate in the study, were invited to extract one of the sealed envelopes that contained the assignment code to any of the three interventions. A treatment adherence diary was provided to the participant. In the diary, adherence to treatment was recorded day by day and the participant recorded each taking of the intervention, as well as the discomfort that she might feel daily. The indication to take each of the capsules was: "take one capsule from bottle 1 and one from bottle 2 and ingest them with liquid in the first bite of breakfast, one from bottle 3 with the first bite of food and one from bottle 4 and another from jar 5 with the first bite of dinner only Once the first visit was concluded, each patient was asked to come within the next 30 ± 3 days and was asked to keep the attachment diary, as well as the bottles to count the capsules consumed, it is in this visit in which were given the food recommendations that appear in the food guidance guide of the Ministry of Health.⁶³

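### Liver disease bars entry and is a ground for elimination, but the plan lists no liver test, so only known or clinically evident disease can be found and tolerability cannot show silent hepatic change

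*Combined protocol and SAP*

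**What the plan says.** In the combined protocol and SAP, the list of people not to be included (under Inclusion criteria) names "DM2, Kidney and / or liver disease, Intolerance to bezafibrate or BBR". Total cholesterol, triglycerides, BMI and blood pressure have numerical limits in that list. Liver disease has no definition, test or limit. The Elimination criteria add "Presence of any non-inclusion criteria during the intervention", so liver disease that appears on treatment is also a ground for removal.

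Under Scrutiny, each candidate had a clinical history and a full physical examination, and the section states that "all the clinical characteristics required for the evaluation of the selection criteria for admission were corroborated". The 5 ml blood sample at that visit was taken "to determine the lipid profile (CT, TG, HDL-C) and glucose". The Intervention period section then says: "Through the indicated laboratory tests, each of the biochemical selection criteria was identified and documented".

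Laboratory determinations gives methods for total cholesterol, triglycerides, HDL-C, calculated LDL-C and VLDL, glucose, creatinine and uric acid. The non-lipid outcomes are "Secondary: weight, height, BMI, WC, BP, glucose, creatinine and uric acid, as well as tolerability". The final visit, at 90 ± 3 days, repeats the starting measurements. Tolerability information comes from a patient diary, questioning at visits, and examination when needed or when an adverse event is suspected.

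**The concern.** A criterion that works both at entry and during treatment needs some means of ascertainment. For liver disease the plan offers only history and examination, which can miss disease without symptoms or signs.

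Two things could be lost. The first is participant protection: someone with unrecognised liver disease could take the study treatment for 90 days. The protocol itself gives reasons to care. The Introduction names fatty liver among the complications of hypertriglyceridemia, which every participant has by definition. The Background calls this the first study of the combination for mixed dyslipidemia, and Ethical aspects classes it as above minimal risk.

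The second is the meaning of the tolerability result. Symptoms and signs can be described, but a favourable summary would carry no information about silent hepatic change in any arm.

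**Working it through.** The check is mainly a comparison of every place where a liver test could be listed.

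- Screening draw (Scrutiny): lipids and glucose. No liver marker.
- Assay methods (Laboratory determinations): lipids, glucose, creatinine, uric acid. No liver marker.
- Outcome variables (Dependent variables): the lipid profile plus the secondary list quoted above. No liver marker.
- Visits at days 30 and 60: diary review, capsule count, questioning. No blood draw is described.
- Day 90: a repeat of the starting set, so again no liver marker.
- Annexes: the body cites them for dietary recommendations and consent, not for laboratory tests.

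No aminotransferase, bilirubin, serology or liver imaging appears anywhere in the text.

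The participant flow does not settle the matter. Of 60 people screened at the institute, 21 did not have mixed dyslipidemia, and "Of the 39 who met the criteria for mixed dyslipidemia, 3 decided not to participate in the study and 36 agreed to participate". The sum closes: 21 + 3 + 36 = 60. Nobody is recorded as excluded for liver disease, but nobody is recorded as excluded at this stage under any other non-lipid criterion either. The flow is therefore not evidence of missed cases.

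**Blood available.** The total planned is 10 ml per patient, and screening uses 5 ml. 10 − 5 = 5 ml, enough for one further draw of the same size, which fits the day-90 repeat. Two samples per participant therefore already exist in the plan.

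**Number of runs.** If only the 39 lipid-eligible candidates are tested at screening and all 36 participants return at day 90, each enzyme needs 39 + 36 = 75 runs. If all 60 screened are tested, it is 60 + 36 = 96. Replacing excluded candidates would add to either figure.

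**Recruitment.** There was no slack: 36 people agreed for 36 envelopes. Each participant enrolled took 60/36 ≈ 1.7 institute screenings and, since "15 detection campaigns were carried out in different points of the metropolitan area of Guadalajara, in which 290 people were attended", 290/36 ≈ 8.1 campaign attendees. Each candidate excluded on enzymes would cost about that much to replace, ignoring the chance that the replacement is also over the limit.

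**What the day-90 result could show.** With 12 per arm and no raised values in an arm, the exact two-sided 95% upper limit for the true rate is 1 − 0.025^(1/12) = 0.265, or about 26%. The data would be descriptive only.

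**The case against.** The strongest reply is that the criterion was applied as written. It has no cut-off, it stands beside type 2 diabetes and drug intolerance, which have none either, and it reads naturally as known or clinically evident disease. History and examination suit that meaning. This reading is fair, and it stands. What remains is that the plan does not say so, and that under this reading silent disease is outside the exclusion altogether.

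A second reply is that the screening list may be incomplete. Creatinine is a before-and-after outcome yet is missing from that list, so silence there is weak evidence. That also stands in part. But creatinine does have a method in the assay section, and no liver test does. The supportable statement is that none is listed, not that none was done.

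A third reply is that the documents describe no hepatic hazard from either drug. They call bezafibrate safe and well tolerated, and fatty liver is mentioned as a complication of the lipid disorder. This is correct and limits the weight of the point.

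A reader might infer three stronger things that the documents do not support:

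- That the plan contradicts itself, because it says the biochemical selection criteria were documented by laboratory tests. A criterion without a laboratory value need not be a biochemical one, so no contradiction is shown.
- That some participants had silent liver disease. The documents give no rate. If the rate were 5% to 20%, 36 × 0.05 = 1.8 to 36 × 0.20 = 7.2 people would be expected, but that only restates the assumption.
- That hepatic harm occurred or that the lipid results are biased. Nothing in the text points to either.

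**Conclusion.** The point holds as a gap in ascertainment and in safety reporting. The plan excludes and eliminates for liver disease but lists no liver test at any stage for any of the 36 participants. Only known or clinically evident disease can be found, and the tolerability objective cannot address silent hepatic change.

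Its size in patients cannot be stated. No figure in the documents bears on how many lipid-eligible people would exceed an enzyme limit, and no limit has been set. The primary lipid comparison, its error rate and its power are not touched.

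The conclusion assumes that the body text lists all laboratory work relevant to eligibility. If liver tests were run but not described, the remedy is to report them. This is a worthwhile, low-cost improvement to the plan. It does not put the trial's main result in doubt.

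**What to change.** For a trial still to be run on this plan:

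1. State what counts as liver disease for entry and how it is ascertained.
2. Run ALT and AST on the existing screening blood and apply an upper limit, set by the investigator in advance, before allocation. Lipid results from the same sample are already needed before visit 1.
3. Repeat ALT and AST on the day-90 blood and report both time points by arm, descriptively, under tolerability.

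The day-90 test comes too late to support elimination during treatment. That would need an added draw at day 30 or 60, which is a separate decision and not part of this low-cost change.

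The text describes the trial as already conducted. If enzymes cannot be run on stored samples, the report should say that liver disease was judged by history and examination, describe tolerability as based on symptoms and examination, and make no hepatic safety claim. That costs a sentence or two.

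The cost of testing is about 75 or more runs of each enzyme, assuming that the existing analyser can do them, with no new draw for those enrolled. A few more people may need to be screened, at about 1.7 institute screenings per candidate replaced. Two limits remain: normal enzymes do not rule out silent liver disease, and 12 per arm is too few for any firm statement about hepatic safety.

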The third group of 12 patients with mixed dyslipidemia received 200 mg of Bezafibrate in the morning with 500 mg of BBR, a 500 mg capsule of BBR in the meal and finally a 200 mg capsule of bezafibrate and a 500 mg of BBR at night.

During the visit at the beginning of the intervention period, all participants who met the inclusion criteria and agreed to participate in the study were asked to select a sealed envelope of 36; 12 sachets from group 1, 12 from group 2 and 12 from group 3, which were mixed. At the time of selection, they were all equal with a number corresponding to each intervention group. Once scrambled, they were arranged in a box and the patient took one at random.

The opening of the envelope selected by each participant allowed to know a numerical code that identified the intervention that the participant received. Blinding was guaranteed in which the participant was unaware of the type of

treatment received, as well as the investigator. At the end of the study when the data were completed, the treatment codes were opened for statistical analysis, this without the person in charge of carrying out the statistical analysis knowing the treatment that the participants received. Participants who left the study without having completed the procedures, but who received at least one dose of the intervention, were taken into account for statistical analysis.

Clinical determinations

All the anthropometric and vital signs determinations as well as the procedures for the interrogation of the physical examination and the integration of the corresponding clinical history were carried out using accepted universal methods and in accordance with the General Health Law in its regulations on the presentation of care services medical.

The physical examination as well as the clinical questioning were performed again on all the occasions required within the development of the study or when adverse events were suspected, which were also directly recorded in the attachment diary of each participant.

Age: defined as the number of years elapsed since the patient's date of birth
Gender: considered as the phenotypic sex of the participant at the time of birth and registered as female or male

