Visits 2 and 3. They were carried out on days 30 and 60 ± 3 days after starting treatment. During these visits, the treatment adherence diary was reviewed, the capsule consumption record in the adherence diary and the number of capsules that were in each of the bottles were counted, and likewise, the patient was questioned to identify the possible presence of adverse events and were recorded in the file of each participant. The doubts that each patient might have were solved, they were reiterated about any doubts that the participant might have at the time, the bottles were collected, the capsules contained in each of them were quantified, the happy faces marked in the Attachment diary and finally the patient was given treatment for one more month. An appointment was made in 90 ± 3 days.

End of the intervention period 90 ± 3 days after the start of the intervention period. The clinical and laboratory measurements were taken again as at the beginning of the project. Adherence to treatment was evaluated

ETHICAL ASPECTS

The study is classified according to the Regulation of the General Health Law on Research for Health, in its Third Title, Chapter I, Article 64 as a study with greater than minimal risk, for which it required signing of consent under information of each participant (see ANNEX).

The procedures adhered to the ethical norms, the Regulations of the General Health Law in Research Matters and the principles emanating from the 18th Medical Assembly of Helsinki, Finland in 1964 and the modifications made by said Assembly in Tokyo Japan in 1975, in Venice, Italy in 1983, in Hong Kong in 1989 and the 48th General Assembly of Somerset West, Republic of South Africa in 1996, 59th General Assembly, Seoul, Korea, October 2008 64th General Assembly, Fortaleza, Brazil, October 2013 where the medical research (clinical research). The study qualified for research in humans.¹⁹

- In accordance with the guidelines of good clinical practice, all participants in the study were identified only by initials and number in the electronic database. The data was kept confidential, as were the results of clinical and laboratory tests, to ensure privacy. The results of this study are presented in this work, without indicating information that could reveal the identity of the participants.⁶⁵

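### Dosed participants who leave before day 90 are to be analysed, but the plan describes no way for them to have a final lipid value

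*Combined protocol and SAP*

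**What the plan says.** **Who is analysed.** Elimination criteria lists withdrawn consent, loss to follow-up, a serious adverse event and adherence below 80%, which "were considered as a reason for exclusion, but not so in the final statistical analysis". A separate sentence follows with no analysis rule of its own: "Presence of any non-inclusion criteria during the intervention". Groups, intervention allocation and blinding is clearer. "Participants who left the study without having completed the procedures, but who received at least one dose of the intervention" are to be counted in the statistical analysis.

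**When lipids are measured.** Lipids, the primary outcome, are sampled at screening (Scrutiny). Visits 2 and 3, at days 30 and 60, list diary review, capsule counts, adverse-event questions and resupply, and no blood draw. At day 90 ± 3, "The clinical and laboratory measurements were taken again as at the beginning of the project".

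**How lipids are tested.** The Statistic Analysis Plan specifies a "Wilcoxon rank test to identify differences between the baseline and final evaluation of each intervention group", a Kruskal-Wallis test across the three groups, and a "Mann-Whitney U test to identify differences between two intervention groups in relation to the quantitative variables". It states no rule for missing values.

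**The concern.** The plan promises to analyse participants for whom it describes no outcome. The Wilcoxon test needs a baseline and a final value. A between-group test of treatment effect needs a final value, whether it compares final levels or changes. A person who leaves on day 40 has only a baseline. Dropping that person departs from the two statements on who is analysed. Keeping that person needs a value that the plan does not define, and the choice would be made after the data are seen.

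The main stake is bias. Leaving after a serious adverse event or for intolerance can depend on the treatment received, so final values need not be lost equally or at random across the three arms. With 12 per arm, each missing value also costs some power.

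**Working it through.** **Step 1. Is there any other post-baseline lipid value?** None is described. Laboratory determinations gives 10 ml of blood per patient for the whole study, and Scrutiny takes 5 ml. The remaining 10 − 5 = 5 ml fits one later draw, if that draw is also 5 ml (an assumption, since its volume is not given).

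**Step 2. Which elimination reasons leave a gap?**

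| Reason | Day-90 value? |
|---|---|
| Consent withdrawn before day 90 | None, and a protocol rule cannot recover it |
| Lost to follow-up | None, and largely not recoverable |
| Serious adverse event | Not stated whether the day-90 visit is kept; recoverable if it is |
| Adherence below 80%, attends day 90 | Yes, so not affected |
| Non-inclusion criterion met, participant leaves | As for a serious adverse event; the allocation section covers the analysis |
| Non-inclusion criterion met, participant stays | Yes, but the analysis rule is unclear |

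On adherence, Visits 2 and 3 state no threshold for continuing and close with "finally the patient was given treatment for one more month". The end visit is where "Adherence to treatment was evaluated". Low adherence may therefore be judged only when a final value already exists.

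**Step 3. Reproduce the plan's sample size.** The inputs, from the sample-size text under Study site, are z = 1.96 and 0.842, SD 35 mg/dL and a TG difference of 44.2 mg/dL.

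n = 2 × (1.96 + 0.842)² × 35² / 44.2² = 9.85, so 10 per arm. Adding 20% gives 10 × 1.2 = 12. The plan's figures reproduce.

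**Step 4. Power cost of missing values on that formula.** Power = Φ(44.2 / (35 × √(2/n)) − 1.96), with n final values per arm:

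- n = 12: Φ(1.133) = 87.1%
- n = 10: Φ(0.864) = 80.6%
- n = 9: Φ(0.719) = 76.4%

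**Step 5. The planned test.** A simulated Mann-Whitney test used 200,000 runs per pair, normal data with the same SD and difference, and exact two-sided p ≤ 0.05. Power was about 80.6% at 12 v 12, 78.3% at 11 v 12 and 71.5% at 10 v 10. One lost value costs 80.6 − 78.3 = 2.3 points. Using ranks instead of the z formula costs 87.1 − 80.6 = 6.5 points at 12 v 12 with nothing missing. Normal data is an assumption, because the Statistic Analysis Plan reports that TG was not normally distributed.

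None of these figures measures bias, which cannot be computed from the documents.

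**The case against.** **The trial may have no such participant.** The text reports 36 who agreed to take part, treatment codes opened once the data were complete, and a normality test already run. It mentions no leaver. This stands in part: the actual effect cannot be judged, and prospective rules may come too late. Whether all 36 gave a final value is still not reported.

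**Counting leavers in the analysis need not mean the lipid tests.** They can contribute to tolerability, which is an objective, and to baseline summaries. That is a sensible reading, but the plan does not say so, and the elimination sentence is loosely worded. The fix adopts this reading explicitly.

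**Losses were budgeted.** This is correct for sample size: two losses per arm leave 80.6% on the plan's formula. An allowance for numbers does not remove bias from selective loss.

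Three stronger readings are tempting and are not supported:

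- A reader might infer that every eliminated participant lacks a final value. The documents never say that elimination cancels the day-90 visit, and low adherers who attend have a value.
- A reader might infer from Step 5 that a single missing value takes the trial below 80% power. The exact rank test starts at only about 80.6% with nothing missing. Most of the shortfall comes from sizing with a z formula and testing with ranks, which is a separate matter.
- A reader might infer that the results are biased in a known direction. Nothing in the documents shows this.

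**Conclusion.** The concern holds for participants who actually leave before day 90. The plan says that they are analysed but describes no final lipid value for them, so they cannot enter the final-value tests. The avoidable part is mainly those who leave after a serious adverse event or for intolerance, since withdrawn consent and loss to follow-up largely cannot be cured by a rule.

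The bias is possible, but its size and direction are unknown. The power cost is modest and, on the plan's formula, covered up to two losses per arm. The conclusion assumes that the described visits are complete; the annexes are not in the supplied text. This should be fixed because the remedy is cheap, not because harm to the results has been shown.

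**What to change.** 1. State that elimination does not end outcome follow-up. Take the scheduled day-90 sample from every randomised participant who has not withdrawn consent, and keep every observed day-90 value in the assigned group.
2. Amend Elimination criteria and the allocation section to say that dosed participants without a day-90 value count for tolerability and baseline summaries, but are not in the Kruskal-Wallis, Wilcoxon or Mann-Whitney tests of final values. Reconcile the non-inclusion sentence with the allocation section, so that a participant who meets such a criterion, stays and has a day-90 value is clearly covered.
3. Report missing day-90 values by arm and reason.
4. If any are missing, repeat the between-group tests with missing values at opposite extremes in the two arms compared (worst in one and best in the other, then reversed). Giving both arms the same extreme does not bound the comparison. Repeat the Wilcoxon test with missing changes at each extreme.

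The cost is a few sentences of protocol text and a day-90 visit for a few participants. If follow-up is already over, only the retention of observed values, the table and the sensitivity check apply. When treatment itself stops is a clinical matter and is not addressed here.
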